APPENDIX 8 Management of Atezolizumab-Specific Adverse Events (cont.)

INFUSION-RELATED REACTIONS

No premedication is indicated for the administration of Cycle 1 of atezolizumab. However, patients who experience an infusion-related reaction (IRR) with Cycle 1 of atezolizumab may receive premedication with antihistamines or antipyretics/analgesics (e.g., acetaminophen) for subsequent infusions. Metamizole (dipyrone) is prohibited in treating atezolizumab-associated IRRs because of its potential for causing agranulocytosis.

Guidelines for medical management of IRRs during Cycle 1 are provided in [Table 7](#). For subsequent cycles, IRRs should be managed according to institutional guidelines.

Table 7 Management Guidelines for Infusion-Related Reactions

Event	Management
IRR, Grade 1	
 • Reduce infusion rate to half the rate being given at the time of event onset. • After the event has resolved, the investigator should wait for 30 minutes while delivering the infusion at the reduced rate. • If the infusion is tolerated at the reduced rate for 30 minutes after symptoms have resolved, the infusion rate may be increased to the original rate.
IRR, Grade 2	
 • Interrupt atezolizumab infusion. • Administer aggressive symptomatic treatment (e.g., oral or IV antihistamine, anti-pyretic medication, glucocorticoids, epinephrine, bronchodilators, oxygen). • After symptoms have resolved to baseline, resume infusion at half the rate being given at the time of event onset. • For subsequent infusions, consider administration of oral premedication with antihistamines, anti-pyretics, and/or analgesics and monitor closely for IRRs.
IRR, Grade 3 or 4	
 • Stop infusion. • Administer aggressive symptomatic treatment (e.g., oral or IV antihistamine, anti-pyretic, glucocorticoids, epinephrine, bronchodilators, oxygen). • Permanently discontinue atezolizumab and contact Medical Monitor.^a

IRR=infusion-related reaction.

^a Resumption of atezolizumab may be considered in patients who are deriving benefit and have fully recovered from the immune-related event. Patients can be re-challenged with atezolizumab only after approval has been documented by both the investigator (or an appropriate delegate) and the Medical Monitor.

APPENDIX 8

Management of Atezolizumab-Specific Adverse Events (cont.)

PANCREATIC EVENTS

Symptoms of abdominal pain associated with elevations of amylase and lipase, suggestive of pancreatitis, have been associated with the administration of atezolizumab. The differential diagnosis of acute abdominal pain should include pancreatitis. Appropriate work-up should include an evaluation for ductal obstruction, as well as serum amylase and lipase tests. Management guidelines for pancreatic events, including pancreatitis, are provided in [Table 8](#).

Table 8 Management Guidelines for Pancreatic Events, Including Pancreatitis

Event	Management
Amylase and/or lipase elevation, Grade 2	
 • Continue atezolizumab. • Monitor amylase and lipase weekly. • For prolonged elevation (e.g., > 3 weeks), consider treatment with 10 mg/day oral prednisone or equivalent.
Amylase and/or lipase elevation, Grade 3 or 4	
 • Withhold atezolizumab for up to 12 weeks after event onset.^a • Refer patient to GI specialist. • Monitor amylase and lipase every other day. • If no improvement, consider treatment with 1–2 mg/kg/day oral prednisone or equivalent. • If event resolves to Grade 1 or better, resume atezolizumab.^b • If event does not resolve to Grade 1 or better while withholding atezolizumab, permanently discontinue atezolizumab and contact Medical Monitor.^c • For recurrent events, permanently discontinue atezolizumab and contact Medical Monitor.^c

GI = gastrointestinal.

^a Atezolizumab may be withheld for a longer period of time (i.e., > 12 weeks after event onset) to allow for corticosteroids (if initiated) to be reduced to ≤ 10 mg/day oral prednisone or equivalent. The acceptable length of the extended period of time must be agreed upon by the investigator and the Medical Monitor.

^b If corticosteroids have been initiated, they must be tapered over ≥ 1 month to ≤ 10 mg/day oral prednisone or equivalent before atezolizumab can be resumed.

^c Resumption of atezolizumab may be considered in patients who are deriving benefit and have fully recovered from the immune-related event. Patients can be re-challenged with atezolizumab only after approval has been documented by both the investigator (or an appropriate delegate) and the Medical Monitor.

APPENDIX 8
Management of Atezolizumab-Specific Adverse Events (cont.)

Table 8 Management Guidelines for Pancreatic Events, Including Pancreatitis (cont.)

Event	Management
Immune-related pancreatitis, Grade 2 or 3	
 • Withhold atezolizumab for up to 12 weeks after event onset. ^a • Refer patient to GI specialist. • Initiate treatment with 1–2 mg/kg/day IV methylprednisolone or equivalent and convert to 1–2 mg/kg/day oral prednisone or equivalent upon improvement. • If event resolves to Grade 1 or better, resume atezolizumab. ^b • If event does not resolve to Grade 1 or better while withholding atezolizumab, permanently discontinue atezolizumab and contact Medical Monitor. ^c • For recurrent events, permanently discontinue atezolizumab and contact Medical Monitor. ^c
Immune-related pancreatitis, Grade 4	
 • Permanently discontinue atezolizumab and contact Medical Monitor. ^c • Refer patient to GI specialist. • Initiate treatment with 1–2 mg/kg/day IV methylprednisolone or equivalent and convert to 1–2 mg/kg/day oral prednisone or equivalent upon improvement. • If event does not improve within 48 hours after initiating corticosteroids, consider adding an immunosuppressive agent. • If event resolves to Grade 1 or better, taper corticosteroids over ≥ 1 month.

GI = gastrointestinal.

^a Atezolizumab may be withheld for a longer period of time (i.e., > 12 weeks after event onset) to allow for corticosteroids (if initiated) to be reduced to ≤ 10 mg/day oral prednisone or equivalent. The acceptable length of the extended period of time must be agreed upon by the investigator and the Medical Monitor.

^b If corticosteroids have been initiated, they must be tapered over ≥ 1 month to ≤ 10 mg/day oral prednisone or equivalent before atezolizumab can be resumed.

^c Resumption of atezolizumab may be considered in patients who are deriving benefit and have fully recovered from the immune-related event. Patients can be re-challenged with atezolizumab only after approval has been documented by both the investigator (or an appropriate delegate) and the Medical Monitor.

DERMATOLOGIC EVENTS

Treatment-emergent rash has been associated with atezolizumab. The majority of cases of rash were mild in severity and self-limited, with or without pruritus. A dermatologist should evaluate persistent and/or severe rash or pruritus. A biopsy should

APPENDIX 8

Management of Atezolizumab-Specific Adverse Events (cont.)

be considered unless contraindicated. Management guidelines for dermatologic events are provided in [Table 9](#).

Table 9 Management Guidelines for Dermatologic Events

Event	Management
Dermatologic event, Grade 1	
 • Continue atezolizumab. • Consider treatment with topical corticosteroids and/or other symptomatic therapy (e.g., antihistamines).
Dermatologic event, Grade 2	
 • Continue atezolizumab. • Consider patient referral to dermatologist. • Initiate treatment with topical corticosteroids. • Consider treatment with higher-potency topical corticosteroids if event does not improve.
Dermatologic event, Grade 3	
 • Withhold atezolizumab for up to 12 weeks after event onset. ^a • Refer patient to dermatologist. • Initiate treatment with 10 mg/day oral prednisone or equivalent, increasing dose to 1–2 mg/kg/day if event does not improve within 48–72 hours. • If event resolves to Grade 1 or better, resume atezolizumab. ^b • If event does not resolve to Grade 1 or better while withholding atezolizumab, permanently discontinue atezolizumab and contact Medical Monitor. ^c
Dermatologic event, Grade 4	
 • Permanently discontinue atezolizumab and contact Medical Monitor. ^c

^a Atezolizumab may be withheld for a longer period of time (i.e., > 12 weeks after event onset) to allow for corticosteroids (if initiated) to be reduced to ≤ 10 mg/day oral prednisone or equivalent. The acceptable length of the extended period of time must be agreed upon by the investigator and the Medical Monitor.

^b If corticosteroids have been initiated, they must be tapered over ≥ 1 month to ≤ 10 mg/day oral prednisone or equivalent before atezolizumab can be resumed.

^c Resumption of atezolizumab may be considered in patients who are deriving benefit and have fully recovered from the immune-related event. Patients can be re-challenged with atezolizumab only after approval has been documented by both the investigator (or an appropriate delegate) and the Medical Monitor.

NEUROLOGIC DISORDERS

Myasthenia gravis and Guillain-Barré syndrome have been observed with single-agent atezolizumab. Patients may present with signs and symptoms of sensory and/or motor neuropathy. Diagnostic work-up is essential for an accurate characterization to differentiate between alternative etiologies. Management guidelines for neurologic disorders are provided in [Table 10](#).

APPENDIX 8
Management of Atezolizumab-Specific Adverse Events (cont.)

Table 10 Management Guidelines for Neurologic Disorders

Event	Management
Immune-related neuropathy, Grade 1	
 • Continue atezolizumab. • Investigate etiology.
Immune-related neuropathy, Grade 2	
 • Withhold atezolizumab for up to 12 weeks after event onset. ^a • Investigate etiology. • Initiate treatment as per institutional guidelines. • If event resolves to Grade 1 or better, resume atezolizumab. ^b • If event does not resolve to Grade 1 or better while withholding atezolizumab, permanently discontinue atezolizumab and contact Medical Monitor. ^c
Immune-related neuropathy, Grade 3 or 4	
 • Permanently discontinue atezolizumab and contact Medical Monitor. ^c • Initiate treatment as per institutional guidelines.
Myasthenia gravis and Guillain-Barré syndrome (any grade)	
 • Permanently discontinue atezolizumab and contact Medical Monitor. ^c • Refer patient to neurologist. • Initiate treatment as per institutional guidelines. • Consider initiation of 1–2 mg/kg/day oral or IV prednisone or equivalent.

^a Atezolizumab may be withheld for a longer period of time (i.e., > 12 weeks after event onset) to allow for corticosteroids (if initiated) to be reduced to ≤ 10 mg/day oral prednisone or equivalent. The acceptable length of the extended period of time must be agreed upon by the investigator and the Medical Monitor.

^b If corticosteroids have been initiated, they must be tapered over ≥ 1 month to ≤ 10 mg/day oral prednisone or equivalent before atezolizumab can be resumed.

^c Resumption of atezolizumab may be considered in patients who are deriving benefit and have fully recovered from the immune-related event. Patients can be re-challenged with atezolizumab only after approval has been documented by both the investigator (or an appropriate delegate) and the Medical Monitor.

IMMUNE-RELATED MENINGOENCEPHALITIS

Immune-related meningoencephalitis is an identified risk associated with the administration of atezolizumab. Immune-related meningoencephalitis should be suspected in any patient presenting with signs or symptoms suggestive of meningitis or encephalitis, including, but not limited to, headache, neck pain, confusion, seizure, motor or sensory dysfunction, and altered or depressed level of consciousness. Encephalopathy from metabolic or electrolyte imbalances needs to be distinguished from potential meningoencephalitis resulting from infection (bacterial, viral, or fungal) or progression of malignancy, or secondary to a paraneoplastic process.

APPENDIX 8
Management of Atezolizumab-Specific Adverse Events (cont.)

All patients being considered for meningoencephalitis should be urgently evaluated with a CT scan and/or MRI scan of the brain to evaluate for metastasis, inflammation, or edema. If deemed safe by the treating physician, a lumbar puncture should be performed and a neurologist should be consulted.

Patients with signs and symptoms of meningoencephalitis, in the absence of an identified alternate etiology, should be treated according to the guidelines in [Table 11](#).

Table 11 Management Guidelines for Immune-Related Meningoencephalitis

Event	Management
Immune-related meningoencephalitis, all grades	
 • Permanently discontinue atezolizumab and contact Medical Monitor.^a • Refer patient to neurologist. • Initiate treatment with 1–2 mg/kg/day IV methylprednisolone or equivalent and convert to 1–2 mg/kg/day oral prednisone or equivalent upon improvement. • If event does not improve within 48 hours after initiating corticosteroids, consider adding an immunosuppressive agent. • If event resolves to Grade 1 or better, taper corticosteroids over ≥ 1 month.

^a Resumption of atezolizumab may be considered in patients who are deriving benefit and have fully recovered from the immune-related event. Patients can be re-challenged with atezolizumab only after approval has been documented by both the investigator (or an appropriate delegate) and the Medical Monitor.

1. LIST OF ABBREVIATIONS

Abbreviation	Definition
ALK	anaplastic lymphoma kinase
ATA	anti-therapeutic antibody
Baseline	last available data obtained prior to patients receiving the first dose of study drug. In case of multiple assessments, average will be taken
CR	complete response
CT	computed tomography
CTCAE	Common Terminology Criteria for Adverse Events
DOR	duration of response
ECOG	Eastern Cooperative Oncology Group
eCRF	electronic Case Report Form
HR	hazard ratio
ICH	International Conference on Harmonisation
IgG1	immunoglobulin G subclass 1
IMP	investigational medicinal product
ITT	intent-to-treat
IRB	Institutional Review Board
IV	Intravenous
IxRS	interactive voice/Web response system
KM	Kaplan-Meier
ML	mutational load
MRI	magnetic resonance imaging
MTD	maximum tolerated dose
NaF-PET	sodium fluoride positron emission tomography
NCI	National Cancer Institute
NGS	next-generation sequencing
NSCL	C non-small cell lung cancer
ORR	objective response rate
OS	overall survival
PBMC	peripheral blood mononuclear cell
PD	progressive disease
PD-1	programmed death-1
PD-L	1 programmed death-ligand 1
PFS	progression-free survival
PK	pharmacokinetic
PR	partial response
q21d	every 21 days
RCC	renal cell carcinoma

2. BACKGROUND

[figure not shown]
(See protocol background section for study scientific background)

This document specifies the statistical analyses for Study ML39237.

3. STUDY DESIGN

This is a Phase II, open-label, prospective, multicenter study designed to evaluate the efficacy and safety of single-agent atezolizumab as a first-line therapy in patients with locally advanced or metastatic NSCLC. In addition, the primary biomarker objective is to measure bTMB and evaluate whether it can predict for improved clinical outcome with atezolizumab.

There will be approximately 150 patients with Stage IIIB–IVB, locally advanced or metastatic, EGFR/ALK–negative NSCLC (any histology) who are immunotherapy-naïve enrolled at approximately 25–30 study sites in the United States. In case there are patients who are determined to be EGFR/ALK–positive by retrospective blood analysis, recruitment will continue until 150 patients who are negative for EGFR and ALK are enrolled.

AJCC = American Joint Committee on Cancer; Dx = diagnosis; ECOG = Eastern Cooperative Oncology Group; EGFR/ALK = epidermal growth factor receptor/anaplastic lymphoma kinase; IASLC = International Association for the Study of Lung Cancer; IV = intravenous; mets = metastases; NSCLC = non-small cell lung cancer; PD = progressive disease; PS = performance status; q3w = once every three weeks; RECIST = Response Evaluation Criteria in Solid Tumors.

^a Staging criteria based on the IASLC Lung Cancer Staging Project proposed for the eighth edition of the AJCC NSCLC staging system (see Appendix 3). Patients with histologically or cytologically confirmed Stage IIIB-IV NSCLC based on the seventh edition of the AJCC NSCLC staging system are also eligible for study entry.

^b Blood samples will be taken at baseline and at progression (all samples will be tested retrospectively).

^c Treatment beyond RECIST v1.1 progression may be permitted if the patient continues to derive clinical benefit as determined by the investigator.

Atezolizumab (fixed dose of 1200 mg) will be administered intravenously on Day 1 of each 21-day cycle.

Patients who meet the Response Evaluation Criteria in Solid Tumors (RECIST) v1.1 criteria for progressive disease (PD) at any timepoint during treatment will be permitted to continue atezolizumab treatment if there is evidence of clinical benefit, defined as meeting all of the following criteria:

- Evidence of clinical benefit as assessed by the investigator
- Absence of symptoms and signs (including worsening of laboratory values [e.g. new or worsening hypercalcemia]) indicating unequivocal progression of disease
- No decline in ECOG performance status that can be attributed to disease progression
- Absence of tumor progression at critical anatomical sites (e.g., leptomeningeal disease) that cannot be managed by protocol-allowed medical interventions

Patients for whom approved therapies exist must provide written consent to acknowledge deferring these treatment options in favor of continuing study drug at the time of initial progression.

When a patient discontinues study drug, regardless of the reason for discontinuation, the patient will be asked to return to the clinic within 30 days after the last dose of study drug for a treatment discontinuation visit. Patients who discontinue will not be replaced.

Screening tests and evaluations will be performed within 28 days prior to treatment initiation.

Blood samples will be collected at screening, baseline, during therapy, and at first evidence of radiographic disease progression or loss of clinical benefit. Data from the latter blood draws will be used to explore whether the radiographic findings are consistent with changes in *bTMB* as measured by the blood-based diagnostic assays and to explore possible mutational mechanisms of resistance. Additional blood samples may be taken at each scan as defined in protocol Appendix 1.

Tissue biopsies (tissue blocks preferred) may be submitted at any time during the study, with biopsies from diagnosis (archival or fresh) and at progression preferred. For patients who provide tissue samples, next generation sequencing (NGS) may be performed by Foundation Medicine. Results may not be available for samples that do not meet testing criteria. Patients who are unable to undergo biopsy sample collection but otherwise meet the eligibility criteria may still be enrolled to receive atezolizumab.

All patients will undergo tumor assessment at baseline and every 6 weeks (\pm 7 days) thereafter regardless of dose delays for the first 12 months following Cycle 1, Day 1. After 12 months, tumor assessment will be required every 9 weeks (\pm 7 days); tumor assessments will continue until disease progression per RECIST v1.1 or loss of clinical benefit, consent withdrawal, study discontinuation, study completion or death, whichever occurs first. All patients will be followed for survival and anti-cancer therapy while in the study and will be given the option of participating in a long-term follow-up during which survival data will be collected from public resources (e.g., death dates from online obituaries or the National Death Index).

Safety will be assessed on the basis of vital sign measurements, ECOG performance status scores, physical examination findings, clinical laboratory test results, and the frequency, severity, and relationship to atezolizumab of adverse events.

3.1 Protocol Synopsis

The protocol synopsis (see protocol).

3.2 Objectives and Endpoints:

The objectives and corresponding endpoints for the study are outlined in table below.

Objectives	Corresponding Endpoints
Primary Efficacy Objective:	
To evaluate the clinical efficacy of Atezolizumab	ORR according to RECIST v1.1 as assessed by the investigator
Secondary Efficacy Objective:	
To evaluate the efficacy of Atezolizumab	Investigator-assessed PFS according to RECIST v1.1
	Investigator-assessed disease control rate and duration of response according to RECIST v1.1
	Overall survival
Safety Objective:	
To evaluate the safety and tolerability of atezolizumab	Incidence of adverse events, with severity determined through use of NCI CTCAE v4.0
Primary Biomarker Objectives:	
To evaluate whether "positive" bTMB (defined as bTMB ≥ 16 , and bTMB ≥ 10) is associated with improved PFS with the treatment of atezolizumab	Relationship between PFS and bTMB (≥ 16 vs < 16) and between PFS and bTMB (≥ 10 vs < 10)
Secondary Biomarker Objective:	
To evaluate whether "positive bTMB" defined at various bTMB cutoff points or quantiles can predict for improved PFS with atezolizumab.	Relationship between PFS and various bTMB cutoff points, defined as range 4 to 24 by twos, and quantiles, except the primary cutoff points 16 and 10
To evaluate the correlation between clinical outcomes including but not limited to PFS rate at 6, 9, and 12 months, ORR, disease control rate and various definitions of positive bTMB.	Relationship between efficacy endpoints including PFS rate at 6, 9, and 12 months, disease control rate, ORR and various bTMB cutoff points and quantiles

Exploratory Biomarker Objectives in Blood:	
To evaluate whether higher expression of an immune-related gene signature in blood PBMCs predicts for improved PFS with atezolizumab	Relationship between PFS and expression of an immune gene signature in PBMCs
To assess whether bTMB is altered as a result of treatment with immunotherapy	Relationship between bTMB and treatment with immunotherapy
To assess the status of additional circulating biomarkers related to immunotherapy and NSCLC and outcomes with atezolizumab	Relationship between circulating biomarkers related to immunotherapy and NSCLC and efficacy
Exploratory Biomarker Objectives in Tissue:	
To perform retrospective tTMB analysis and NGS-based mutation testing on tissue biopsies for patients providing specific consent and viable samples	Relationship between somatic mutations and tTMB on efficacy. All mutations will be identified through NGS performed on DNA extracted from tumor tissue.

3.3 Timing of Analyses

The primary efficacy analysis measured by ORR may be performed after all patients complete 6 months of follow-up (i.e. 6 months after last patient enrolled into the study). If the primary efficacy analysis is not performed at 6 months of follow-up, it will be performed during the final analysis. The final analysis will be performed at the end of the study, 18 months after all patients have been enrolled.

One interim analysis is planned 6 months after one-half of the patients have been enrolled. The purpose of the interim analysis is to provide preliminary results in evaluating the biomarker cutoff and to perform a futility analysis. The futility criteria to stop the study will be met if the true ORR is more likely $\leq 5\%$ rather than $\geq 15\%$, or if 4 or fewer patients have an objective response from the first 75 enrolled and treated patients. The chance of stopping the study is $> 67\%$ if the true ORR is 5% or less. The chance of stopping the study is $< 1\%$ if the true ORR is 15% or larger. No type-1 error adjustments will be made for the interim analysis.

4. STATISTICAL METHODOLOGIES

4.1 Sample size:

The sample size for this study is based on the primary efficacy objective and primary biomarker objectives. Based on 150 patients, the maximum half width of the 2-sided 95% CI of the estimated ORR will be within 8%. Additionally, based on 150 patients, there will be at least 80% power to detect a statistical improvement in PFS for bTMB high group vs bTMB low subgroup. The power listed in the table below is based on the following assumptions: the test is 2-sided, significance level is 0.10, both biomarker subgroups have at least 25% of the patients (i.e., 37 or more patients in both groups), median PFS is 4 months for the subgroup with a shorter median PFS, the HR of PFS between the subgroup with a shorter PFS versus the other subgroup is 0.6 or lower, the recruitment duration is one year, the follow-up time from last patient in is 18 months, and the dropout rate is 5%.

n =150	Power		
	Biomarker ≥ 25th percentile vs.< 25th percentile	Biomarker ≥ 50th percentile vs. < 50th percentile	Biomarker ≥ 75th percentile vs. < 75th percentile
0.4	100%	100%	100%
0.5	97%	99%	97%
0.6	83%	92%	84%
0.7	58%	69%	58%

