6.1 DETERMINATION OF SAMPLE SIZE

The sample size for this study is based on the primary efficacy objective and primary biomarker objective.

Based on 150 patients, the maximum half width of the 2-sided 95% CI of the estimated ORR will be within 8%.

Additionally, based on 120 biomarker-evaluable patients (80% of the study population), with a minimum follow-up of 6 months during the primary analysis, and with 28 patients in the smaller biomarker positive or negative group (19% of the study population), the study primary biomarker analysis will have 89% and 79% power to detect PFS difference if the HRs of PFS between the biomarker positive vs. negative group is 0.50 or 0.55, respectively. The above-mentioned power is for a 2-sided test with a significance level of 0.1, assuming a median PFS of 4 months for the subgroup with a shorter median PFS.

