4.2 Analysis Populations

Efficacy Analysis Population:

The primary Efficacy analyses will include all patients who receive at least one dose of study drug.

Safety Analysis Population:

The safety analyses will be based on all patients who received any dose of atezolizumab during the study treatment period.

Biomarker Analysis Population:

Biomarker analyses will include all patients who receive at least one dose of study drug and have evaluable baseline biomarker assessment.

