4.7 Biomarker Analyses

Biomarker analysis will be based on Biomarker analysis population, which is all patients who receive at least one dose of study drug and have evaluable baseline biomarker assessment, as defined in section 4.2.

The blood tumor mutational burden (bTMB) assay is a blood-based, circulating tumor DNA (ctDNA) next generation sequencing (NGS) test that will be used as an aid in the identification of non-small cell lung cancer (NSCLC) patients most likely to respond to atezolizumab, a

programmed death-ligand (PD-L1) blocking antibody. The NGS-based assay counts the total number of somatic mutations (single nucleotide variants (SNVs) excluding driver mutations) over a 1.25 megabase (Mb) region of coding DNA in ctDNA isolated from fresh plasma derived from whole blood. bTMB is reported as a whole integer score.

The bTMB assay has been analytically validated and clinically validated retrospectively (ESMO 2017 Gandara presentation and Fabrizio poster and manuscript in review). The assay detects SNVs down to 0.5% allele frequency across 394 genes from as little as 1% tumor content in a cell free DNA (cfDNA) sample. Tumor content is estimated by determining the maximum somatic allele frequency (MSAF). All samples in the biomarker evaluable population have MSAF $\geq 1\%$. The FDA approved the IDE for the bTMB assay in 2017, and the assay is now being used to prospectively enroll 1L NSCLC patients in the BFAST trial.

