4.7.1 Primary Biomarker Analyses

K-M curves and a log-rank test will be used to evaluate the differences in PFS between bTMB high versus low groups at 16 and 10 two different cutoff points (i.e. bTMB ≥ 16 vs < 16 , and bTMB ≥ 10 vs < 10). The Gatekeeping testing procedures will be used to test PFS differences at these two primary bTMB cut off points. PFS difference at cutoff point 16 will be tested first. If there is statistical significance in PFS difference bTMB ≥ 16 vs < 16 groups, we will claim statistical significant difference in PFS between bTMB ≥ 16 vs < 16 groups, and we will further test PFS difference at cutoff 10. We can only claim PFS difference between bTMB ≥ 10 vs < 10 groups if both tests for cutoff point 16 and cut off point 10 are statistically significant.

The statistical tests for primary analysis as well as for other analyses comparing efficacy differences between bTMB high group vs low group will be two-sided at a significance level of 0.10. The corresponding bTMB group differences will be estimated and two-sided 90% confidence interval will be provided. All other statistical tests used in the study will be two-sided at level of 0.05. Their corresponding point estimators will be estimated and two-sided 95% confidence interval will be provided.

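### The SAP's power of at least 80% for the bTMB comparison counts all 150 patients; with the protocol's 120 biomarker-evaluable patients it is about 74–77% at HR 0.6 and a 25/75 split

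*SAP*

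**What the plan says.** SAP section 4.1 gives the power for the primary biomarker comparison: "based on 150 patients, there will be at least 80% power to detect a statistical improvement in PFS for bTMB high group" versus the low group. The conditions include a two-sided 0.10 test, a 4-month median in the shorter-PFS group, HR 0.6 or lower, one-year recruitment, 18 months of follow-up after the last patient, 5% dropout, and that "both biomarker subgroups have at least 25% of the patients (i.e., 37 or more patients in both groups". The table is headed n = 150. At HR 0.6 it shows 83%, 92% and 84% for cuts at the 25th, 50th and 75th percentiles.

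The comparison is not run on all 150 patients. SAP section 4.2 says: "Biomarker analyses will include all patients who receive at least one dose of study drug and have evaluable baseline biomarker assessment". SAP section 4.7 adds an assay condition: "All samples in the biomarker evaluable population have MSAF" of at least 1%.

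Protocol section 6.1 computes its own biomarker power "based on 120 biomarker-evaluable patients (80% of the study population), with a minimum follow-up of 6 months during the primary analysis". For the smaller of its two biomarker groups it takes 28 patients, which is 19% of 150 but 23% of the 120 analysed.

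**The concern.** The headcount of 37 in SAP 4.1 is 25% of 150. On 120 evaluable patients, 25% is 30. The SAP moves the power denominator from 120 to 150 without giving an evaluability rate or a reason, while keeping a definition that excludes non-evaluable patients. Its 5% dropout is loss to follow-up and does not stand in for a 20% share with no usable baseline result.

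If 120 is the right figure, the SAP overstates power in the uneven splits that it says it covers. The primary biomarker analysis is also hierarchical: under SAP section 4.7.1, "PFS difference at cutoff point 16 will be tested first", and a difference at cutoff 10 can be claimed only if cutoff 16 is significant. A miss at the first test therefore ends both claims.

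**Working it through.** **Inputs.** From SAP 4.1: two-sided alpha 0.10 (z = 1.645), shorter median 4 months, HR 0.6, accrual A = 12 months, follow-up after last patient F = 18 months, 5% dropout. From protocol 6.1: 120 evaluable patients.

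**Formulas.** Assume exponential PFS and uniform accrual. A patient with hazard λ has an event with probability

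p(λ) = 1 − [exp(−λF) − exp(−λ(F + A))] / (λA).

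With s the share in the shorter-PFS group, expected events are D = N[s·p(λ₁) + (1 − s)·p(λ₂)], and by Schoenfeld's formula

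power = Φ( √(D·s·(1 − s)) · |ln HR| − 1.645 ).

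Here λ₁ = ln 2 / 4 = 0.1733 and λ₂ = 0.6 × 0.1733 = 0.1040 per month, so p(λ₁) = 0.981 and p(λ₂) = 0.912 before dropout. |ln 0.6| = 0.5108.

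**Step 1: reproduce the SAP at N = 150.** For s = 0.25, D = 150 × (0.25 × 0.981 + 0.75 × 0.912) = 139.4. Then √(139.4 × 0.1875) × 0.5108 − 1.645 = 0.967, which gives 83.3%. All three splits at HR 0.6:

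| Dropout coding | 25th | 50th | 75th |
|---|---|---|---|
| SAP table | 83% | 92% | 84% |
| None | 83.3% | 91.9% | 84.5% |
| 5% per year | 82.4% | 91.3% | 83.7% |
| Flat 5% (N × 0.95) | 81.6% | 90.7% | 82.8% |

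The rows for HR 0.4, 0.5 and 0.7 agree to within about 2 points. The table is right for 150 patients, and the model matches the SAP's.

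**Step 2: change only N to 120.** For s = 0.25 and no dropout, D = 111.5. Then √(111.5 × 0.1875) × 0.5108 − 1.645 = 0.691, which gives 75.5%. At HR 0.6:

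| Dropout coding | 25th | 50th | 75th |
|---|---|---|---|
| None | 75.5% | 85.9% | 76.9% |
| 5% per year | 74.5% | 85.1% | 76.0% |
| Flat 5% | 73.6% | 84.3% | 75.0% |

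A log-rank simulation (20,000 runs per cell, 5% dropout per year) gives about 77%, 84% and 73%. It reverses the order of the two uneven splits but leaves both below 80%.

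Other hazard ratios at N = 120 with 5% dropout per year: HR 0.4 gives 99 / >99 / 99%, HR 0.5 gives 92 / 97–98 / 94%, and HR 0.7 gives 49 / 60 / 50% (SAP: 58 / 69 / 58%).

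**Step 3: the protocol's own split.** With 28 of 120 in the smaller group, HR 0.6 and 18 months of follow-up, power is 72–75% (simulation 71–75%).

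**Step 4: how much depends on 120.** At 25/75 and HR 0.6 with 5% dropout per year:

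| Evaluable N | Power (two directions) |
|---|---|
| 120 | 74–76% |
| 130 | 77–79% |
| 135 | 79–80% |
| 140 | 80–81% |
| 150 | 82–84% |

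So 80% needs about 135–140 evaluable, which is 90–93% of 150. With 120 evaluable, 80% is reached at an HR of about 0.575–0.58 for a 25/75 split, or at HR 0.6 once the smaller group is about 30–33%.

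**The case against.** The strongest reply is that the SAP made no arithmetic error. It states N = 150 openly, its table is correct on that basis, and its minimum group is given as a headcount of 37 as well as a share. With 37 of 120 in the smaller group (31%), power at HR 0.6 is 78–81%, so on a headcount reading the promise roughly survives. This is fair. But the SAP's leading condition is 25% and 37 is its gloss on that figure. The two agree only if all 150 patients are evaluable, which SAP 4.2 and 4.7 do not assume.

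Second, 120 is a planning number, and the protocol does not tie it to the SAP's allele-frequency rule. SAP section 3 also lets recruitment continue until 150 EGFR/ALK-negative patients are enrolled, so the total could exceed 150. That stands as a caveat. Even so, 120 is the only evaluable count in either document. At 80% evaluability, the required 135–140 would mean about 169–175 treated patients (135/0.8 to 140/0.8).

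Third, the protocol's design effects are HR 0.50 and 0.55, where a 25/75 split of 120 still gives about 92–94% and 85–86%. HR 0.6 is the edge case. It is, however, the edge that the SAP names as covered.

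Fourth, it does not follow that the first test is the uneven one. The group at or above 16 cannot be larger than the group at or above 10, but neither document gives the bTMB distribution, so it need not be the minority. The finding does not depend on this.

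**Conclusion.** The concern holds. On the planned biomarker population, the stated power of at least 80% at HR 0.6 is not delivered at a 25/75 split. It is about 74–77% by Schoenfeld's formula over three dropout codings and 73–77% by simulation, or 3–7 points below the promise. The chance of missing a true HR of 0.6 rises from the tabulated 16–17% to about 24–26% (23–27% over all variants).

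This rests on 120 evaluable patients, exponential PFS and 18 months of follow-up. It does not extend to a median split, to HR 0.5, or to a smaller group of about a third, where 80% is still met. The fault is the denominator: the table itself is computed correctly. The effect is modest and alters no test, but the SAP promises a power that its own population definition does not support.

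**What to change.** Recompute the SAP 4.1 table for 120 biomarker-evaluable patients, with 30 or more in the smaller group. At HR 0.6, replace the 80% statement with about 75% / 85% / 76% for the 25th / 50th / 75th percentile cuts, noting that simulation puts either uneven split at 73–77%. Alternatively, keep 80% and state when it applies: an HR of about 0.575 or lower at 25/75, or a smaller group of about one-third or more at HR 0.6. If more than 120 evaluable patients are expected, give the number and its basis.

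Two clarifications belong in the same edit:

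- **Direction of the HR.** State it as longer-PFS versus shorter-PFS group. The present wording has it the other way round, which would make the ratio exceed 1.
- **Timing.** Protocol section 6 places the primary biomarker analysis after 6 months of follow-up, while SAP 4.1 computes power at 18 months. SAP 3.3 says "The final analysis will be performed at the end of the study, 18 months after all patients have been enrolled" but does not date the primary biomarker test. State which applies. At 6 months, 120 evaluable patients at 25/75 and HR 0.6 give about 65–70% if accrual takes one year. The protocol states no accrual period; 6 to 24 months gives about 60–74%.

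The cost is one table and a few sentences, with a less favourable power figure at uneven splits. No extra patients are needed and the tests do not change.
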